Research Protocol

Impact of CO₂ on cerebral blood flow in infants under 6 months of age during general anesthesia

Principal investigator:

[name]

Anesthesiologist, CHU Sainte-Justine.

1. *Hypothesis*

Optimal cerebral perfusion is an essential objective during anesthesia, especially in infants, whose brains are immature. A number of factors influence cerebral blood flow (CBF) and cerebral oxygenation: arterial pressure, PaCO₂ and hemoglobin.

We previously showed that a mean arterial pressure (MAP) of between 35 and 45 mm Hg was an intraoperative objective for maintaining safe cerebral oxygenation in normocapnic conditions and in the absence of anemia in infants under 6 months of age. (1-3)

CO₂ influences cerebral vascular tone. Hypocapnia causes vasoconstriction, a decrease in CBF and a risk of cerebral ischemia, while hypercapnia causes vasodilation and an increase in CBF. (4)

Mechanical ventilation during general anesthesia changes PaCO₂. Furthermore, mechanical ventilation can be tricky in cases of lung disease in children requiring the use of high-frequency oscillatory ventilation. As well, surgery can influence mechanical ventilation as a result of pressure exerted on the lungs, either directly (thoracotomy or thoracoscopy) or indirectly via the abdomen (laparoscopy). Endoscopic techniques use insufflation with CO₂, a gas that readily diffuses through the pleura or peritoneum to the infant's blood compartment.

Like hypotension, an unsuitable intraoperative PaCO₂ can cause serious neurological sequelae. (5-7)

2. *Objectives*

Our primary objective is to determine the impact of varying EtCO₂ and, therefore, PaCO₂ on CBF and cerebral oxygenation with a MAP of between 35 and 40 mm Hg in infants under 6 months of age during general anaesthesia

3. *Methodology*

This will be a prospective study involving infants under the age of 6 months admitted to the surgical suite for surgery requiring mechanical ventilation.

During the anesthesia consultation, explanations will be provided regarding the anesthesia protocol used, with special focus on the following:

- The standard anesthesia technique, no change in the drugs administered, especially with regard to sedation and analgesia.
- The noninvasive, painless and adverse effect-free technique for evaluating cerebral perfusion.
- Changing cerebral perfusion in the direction of improvement (increase in EtCO₂ and increase in

CBF).

An information and consent form will be drafted using the REB's template (see appendix).

Cerebral perfusion will be evaluated by:

- Measuring the systolic, diastolic and mean velocities in the middle cerebral artery using transcranial Doppler ultrasound (see example below).

Infant awake and then under general anesthesia. Systolic and diastolic flow is observed in the awake infant. This flow disappears after the induction of general anesthesia.

- Measuring cerebral oxygen saturation using a tissue oxygen saturation sensor placed in the frontal region.

[figure not shown]

INVOS™ OxyAlert™ NIRSensors

Near-infrared spectroscopy (NIRS) is used to noninvasively evaluate regional cerebral oxygen saturation (rSO_2). It reflects the balance between cerebral oxygen supply and consumption (8). A decrease in rSO_2 indicates either an increase in cerebral oxygen consumption ($CMRO_2$) and/or inadequate oxygen supply (decrease in CBF). On the other hand, an increase in rSO_2 could indicate either an increase in CBF or a decrease in $CMRO_2$ caused, for example, by general anesthesia.

Description of study (diagram below)

We will perform a first measurement in the infant while awake. After the induction of general anesthesia and airway control, a series of measurements (Doppler and cerebral oxygen saturation) will be made. The following parameters usually used in anesthesia in infants under 6 months of age will be used for the mechanical ventilation: tidal volume, 8 ml/kg; positive expiratory pressure, 5 mm Hg; and a baseline respiratory rate of 25 to 40 cycles per minute, depending on the infant's age. If necessary, a bolus of ephedrine, 0.5 mg/kg, will be administered if the MAP is less than 35 mm Hg after the induction of anesthesia. Subsequently, two series of measurements with a MAP greater than 35 mm Hg will be made after modifications to the ventilation to effect an increase of 5 mm Hg in the EtCO_2 value. The Doppler and cerebral oxygen saturation measurements and both controlled modifications to the mechanical ventilation are specific to this protocol. All the other aspects of the management are based on standard pediatric anesthetic care.

4. Description of population

- Inclusion criteria

[figure not shown]
This will be a prospective study involving infants under 6 months of age admitted to the surgical suite for surgery requiring orotracheal intubation.

- Exclusion criteria

The exclusion criteria will be as follows: infant over 6 months of age, infant with intracranial pathology or a chronic respiratory disease that causes hypercapnia, parental refusal and surgical emergency.

✓ Anticipated benefits for participants.

The Doppler and cerebral oxygen saturation measurements are noninvasive and painless. The measurements will be made at different CO_2 levels within a range usually observed during general anesthesia in infants (9). In our study, we will vary the CO_2 in the direction of optimizing cerebral perfusion. (Example below with transcranial Doppler: diastolic velocity zero after intubation, and normalization after correcting the MAP and CO_2).

5. Statistical analysis

We will analyze the impact of changes in CO_2 on cerebral oxygen saturation and velocities. The Spearman coefficient of correlation will be used to study the correlations between the cerebral perfusion parameters (cerebral velocities and rSO_2c) and EtCO_2 . An ANOVA will be performed to determine the significant differences in rSO_2c and cerebral velocities according to EtCO_2 .

A change in EtCO_2 of +10 mm Hg could result in a relative increase in rSO_2c of +10%. Therefore, with a mean standard deviation of rSO_2c of 13% observed in the previous studies, we calculate the necessary number of subjects to be 36 (alpha risk = 5%; beta risk = 90%). To ensure that we will be able to analyze 36 patients, we hope to include 60 patients in the study. An interim analysis of the results will be performed after 20 patients have been included.

6. Timetable and funding

For the number of patients to be included ($n=60$), based on the volume of activity in the CHU Sainte Justine's surgical suite, we estimate that the duration of the study will need to be 18 months (3 to 5 patients a month).

The company Covidien is lending the cerebral oxygen saturation monitor and is providing the 60

sensors needed for the study. We will use the Department of Anesthesiology's sonograph.

Patient recruitment, parent explanations and the signing of the consent forms will be looked after by the anesthesiologist/principal investigator.

7. *References*

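### The MAP floor of 35 mm Hg covers the two raised-EtCO2 series but not the post-induction reference, so in infants given ephedrine the +10 mm Hg contrast can mix pressure correction with CO2

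*Protocol*

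**What the plan says.** Section 3 of the Protocol (Description of study) gives the sequence in prose and refers to a diagram. After an awake reading, the first anesthetised series is described as follows: "After the induction of general anesthesia and airway control, a series of measurements (Doppler and cerebral oxygen saturation) will be made". No MAP condition is attached. Ventilator settings come next, and then the pressure rule: "a bolus of ephedrine, 0.5 mg/kg, will be administered if the MAP is less than 35 mm Hg after the induction". The raised-EtCO2 series follow: "Subsequently, two series of measurements with a MAP greater than 35 mm Hg will be made after modifications to the ventilation", each modification aiming at a 5 mm Hg rise. That there are two steps is confirmed by the remark that "both controlled modifications to the mechanical ventilation are specific to this protocol".

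Section 1 states that "A number of factors influence cerebral blood flow (CBF) and cerebral oxygenation: arterial pressure", along with PaCO2 and hemoglobin. It also reports from earlier work that "a mean arterial pressure (MAP) of between 35 and 45 mm Hg was an intraoperative objective for maintaining safe cerebral oxygenation". The objective in section 2 narrows the MAP range to 35 to 40 mm Hg, whereas the methods give a floor of 35 and no ceiling.

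In section 5 the sample size starts from the premise that "A change in EtCO_2 of +10 mm Hg could result in a relative increase in rSO_2c of +10" percent, and the analysis is described thus: "An ANOVA will be performed to determine the significant differences in rSO_2c and cerebral velocities according to EtCO_2".

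**The concern.** The study aims to isolate the effect of CO2. That requires the readings being compared to differ in EtCO2 and to be alike in the other determinants of cerebral perfusion, of which the protocol itself lists arterial pressure first. If the reference may be taken below 35 mm Hg and the later readings may not, then in infants who need ephedrine the change from reference has two causes. The ephedrine threshold is also the lower end of the range the protocol regards as safe for cerebral oxygenation, so correction happens where the protocol has reason to expect pressure to matter.

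The illustration under the anticipated benefits (section 4) shows that the mixture is realistic. It describes a Doppler trace with no diastolic velocity after intubation that recovers once both MAP and CO2 have been corrected. A pair of readings like that cannot say which correction did the work.

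An analysis by EtCO2 level would credit the whole change to CO2. If raising a low MAP improves perfusion, the CO2 effect is overstated in those infants. Infants already above 35 mm Hg at the reference have no such bias.

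**Working it through.** **1. The plan's own figure.** Section 5 gives a difference of 10, an SD of 13 (both in percent, taken as being on one scale), alpha 5% and a beta risk of 90%, read here as 90% power. For two independent means, two-sided:

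n = 2 × (1.960 + 1.282)² × 13² / 10² = 2 × 10.51 × 1.69 = 35.5, rounded up to 36 per group.

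The stated 36 reproduces. The present point does not depend on it, but the calculation shows that the planned effect belongs to a 10 mm Hg change.

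**2. Which contrasts use the reference.** Take the two modifications as successive steps of 5 mm Hg, which agrees with the 10 mm Hg in section 5. The anesthetised levels are then 0 (reference), +5 and +10.

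| Contrast | EtCO2 difference | Uses reference | MAP condition stated |
|---|---|---|---|
| 0 vs +5 | 5 | yes | on one side only |
| +5 vs +10 | 5 | no | on both sides |
| 0 vs +10 | 10 | yes | on one side only |

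Two of the three contrasts use the reference, and the only 10 mm Hg contrast is one of them.

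**3. Form of the bias.** Let f be the share of infants whose reference is taken below 35 mm Hg and who are then corrected, and m the mean rSO2 gain from that correction. Then

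expected 0 vs +10 contrast = CO2 effect + f × m.

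The protocol gives neither f nor m. If correction always precedes the reference, f = 0 and the bias is zero.

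**4. Illustration under assumed values.** Assume f from 10% to 50% and m from 2 to 10 points. Suppose CO2 has no effect, 36 infants are analysed as pairs, and the SD of the within-infant difference is 13 (also assumed; it corresponds to a within-infant correlation of 0.5, since 13 × √(2 × 0.5) = 13). The standard error is 13/√36 = 2.17. With b = f × m, the two-sided 5% test rejects with probability 1 − Φ(1.96 − b/2.17) + Φ(−1.96 − b/2.17).

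| f | m | Bias b (points) | Rejection rate with no CO2 effect |
|---|---|---|---|
| 10% | 2 | 0.2 | 5.1% |
| 25% | 5 | 1.25 | 8.9% |
| 50% | 5 | 2.5 | 21% |
| 50% | 10 | 5.0 | 64% |

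Against the planned effect of 10, the bias runs from negligible to half the effect. The table shows only that the answer turns on quantities the protocol does not supply.

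**5. The MAP ranges side by side.** Background (section 1): 35 to 45. Objective (section 2): 35 to 40. Methods (section 3): above 35, no upper limit. A reading at 43 mm Hg meets the methods and lies in the background range, but falls outside the objective.

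**The case against.** The strongest reply is that the sequence is in the diagram, which is not available here, and that the prose is not a strict timeline. The ventilator settings are listed after the post-induction series, although ventilation presumably starts before or during it. Ephedrine and the reference series share the same time marker, after induction. The word opening the sentence on the raised series puts them after ephedrine; it does not put the reference before it. The objective's 35 to 40 range is not limited to the raised series, so a reference below 35 would fall outside the study's own aim. All of this stands, and it limits the point to what the prose permits.

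A second reply is that an analysis plan could adjust for MAP. This helps little where it matters: in a corrected infant MAP and EtCO2 rise together, so a covariate separates them poorly. A like-for-like reference has to be collected at the bedside, which makes this a protocol matter.

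Third, a shared floor does not equalise MAP. A reference at 36 and a raised series at 55 would both comply. That is correct, and it is why MAP should be recorded at each series and the objective's upper limit kept.

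A reader might also count 36 unconditioned reference readings among 36 × 3 = 108 anesthetised readings at the planned 36 infants and take this as the size of the problem. It is not, because it includes every infant who was already above 35.

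**Conclusion.** The point holds as a defect in what the prose fixes. It places a MAP condition on one side of the main contrast and not on the other, with the pressure correction written in between. In infants who need ephedrine, the reference-based contrasts can therefore combine MAP correction with the CO2 effect. The +5 vs +10 contrast has the same floor on both sides and is less exposed.

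The size is unknown. It depends on the share corrected and the gain from correction, neither of which is in the protocol, and it is zero if correction comes first. A reader might infer that the plan deliberately uses a hypotensive reference, or that the CO2 result will be biased. The document supports neither: the order is ambiguous and the diagram may settle it.

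The difference between 35 to 40 in the objective and above 35 in the methods is a real but minor wording point. A reader might conclude that the objective should simply give up its range to match the methods. That would remove the only MAP ceiling in the objective or methods and so loosen control of the very factor at issue.

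This should be fixed, with medium confidence, because a cheap clarification protects the main contrast. The conclusion assumes two successive 5 mm Hg steps and the post-induction series as the reference.

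**What to change.** In section 3, state that the EtCO2 reference series is taken at the starting ventilation settings, after any MAP correction, and under the same MAP condition as the two later series. In an infant whose post-induction reading came before correction, repeat the series before EtCO2 is raised and keep the uncorrected reading as descriptive only. Record MAP at each series.

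As a minor wording change, use one MAP target in sections 2 and 3. Keep an upper limit in it, and report readings above it rather than excluding them, so that no infants or series are lost.

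The cost is one extra noninvasive reading and a short delay before the EtCO2 increase, in corrected infants only, plus a wording amendment. The sample size, the ephedrine rule and the ventilation steps do not change. If the diagram already shows this order, one sentence in the prose is enough for the first part.

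### Section 5 names a Spearman correlation and an unspecified ANOVA for three anaesthetised readings per infant; if the readings are pooled, the p-values for the CO₂ effect are wrong

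*Protocol*

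**What the plan says.** Section 3 (Description of study) sets out the readings. There is an awake reading: "We will perform a first measurement in the infant while awake". Under anaesthesia, "After the induction of general anesthesia and airway control, a series of measurements (Doppler and cerebral oxygen saturation) will be made". Then, "Subsequently, two series of measurements with a MAP greater than 35 mm Hg will be made after modifications to the ventilation", the aim of those modifications being to raise EtCO₂ by 5 mm Hg. Leaving the awake reading aside, that is three readings per infant under anaesthesia.

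Section 5 names two methods. The first is "The Spearman coefficient of correlation will be used to study the correlations between the cerebral perfusion parameters (cerebral velocities and rSO_2c) and EtCO_2". The second is "An ANOVA will be performed to determine the significant differences in rSO_2c and cerebral velocities according to EtCO_2". Neither sentence mentions the infant as a unit, pairing, repeated measures or within-infant change, and nothing elsewhere in the protocol does.

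The sample size rests on a +10 mm Hg change in EtCO₂ that "could result in a relative increase in rSO_2c of +10"%, "with a mean standard deviation of rSO_2c of 13% observed in the previous studies". From this, "we calculate the necessary number of subjects to be 36 (alpha risk = 5%; beta risk = 90"%).

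**The concern.** The objective in section 2 is the effect of varying EtCO₂. The design answers it by using each infant as its own control. The named methods do not say that the analysis will do the same.

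An ordinary Spearman coefficient treats every pair of values as independent and mixes two things: how infants differ from one another, and how one infant responds when EtCO₂ rises. Only the second is the study question. The ANOVA could be run as repeated-measures, but the text leaves that open. Run as a one-way ANOVA, it would put the between-infant variance into the error term.

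These are the only tests named for the primary objective. The size, and for Spearman the direction, of the error would depend on a spread of starting EtCO₂ that the protocol does not state, so a reader could not interpret the p-value.

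**Working it through.** **1. The plan's own figure.** Inputs from section 5: difference 10, SD 13, alpha 5%. The stated beta risk of 90% makes sense only as 90% power, the 10% is read as 10 points, and the test is taken as two-sided.

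- Independent groups: n = 2 × (13/10)² × (1.960 + 1.282)² = 35.5, so 36 per group.
- Paired, SD 13 per reading, within-infant correlation ρ: n = 35.5 × (1 − ρ). This gives 24.9, 17.8 and 10.7, so 25, 18 and 11 infants, for ρ = 0.3, 0.5 and 0.7. It reaches 36 only at ρ = 0.
- Paired, with 13 taken as the SD of the change: 18.

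So the sample size does not show that a paired analysis was intended.

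**2. One-way ANOVA by step.** For the difference between two step means with 36 infants, an unpaired analysis uses a standard error of 13 × √(2/36) = 3.06. The true one is 3.06 × √(1 − ρ) = 2.56, 2.17 and 1.68 for ρ = 0.3, 0.5 and 0.7. The test is therefore conservative whenever ρ is above 0.

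**3. Pooled Spearman, rough check by hand.** For a pooled correlation the variance is multiplied by about 1 + 2·ρx·ρ, where ρx is the correlation of EtCO₂ readings within an infant. Take steps of 0, 5 and 10 mm Hg (two successive 5 mm Hg rises, consistent with the +10 mm Hg in section 5), starting SD s, and reading noise of SD 1. The steps have variance 50/3 and a mean cross-product of −25/3. Hence ρx = (s² − 8.33)/(s² + 17.67).

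- s = 0: ρx = −0.47; multiplier 0.72 to 0.34 for ρ = 0.3 to 0.7 (conservative).
- s = 3: ρx = 0.03; multiplier 1.02 to 1.04 (close to nominal).
- s = 5: ρx = 0.39; multiplier 1.23 to 1.55, about 8–12% rejection.
- s = 7: ρx = 0.61; multiplier 1.37 to 1.85, about 9–15% rejection.

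**4. Simulation.** There were 6,000 trials per setting, with 36 infants and three readings each. The outcome is an infant effect (variance 169ρ), plus effect × step/10, plus a residual (variance 169(1 − ρ)), with ρ = 0.3, 0.5 and 0.7. EtCO₂ is as in step 3. Ranges are over ρ.

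Rejection with no true effect, nominal 5%:

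| Analysis | Starting EtCO₂ SD (mm Hg) | Rejects |
|---|---|---|
| Pooled Spearman | 0 | 0.2–2% |
| Pooled Spearman | 2 | 2–4% |
| Pooled Spearman | 3 | 4–5% |
| Pooled Spearman | 5 | 7–10% |
| Pooled Spearman | 7 | 9–14% |
| One-way ANOVA by step | any | 0–2% |
| Repeated-measures ANOVA | any | 4.5–5.7% |
| Within-infant correlation | any | 4.5–5.6% |

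Power:

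- 10-point rise: pooled Spearman 88–95% at starting SD 0, 72–73% at SD 3 and 50–52% at SD 5, against 96–100% for within-infant correlation.
- 10-point rise: one-way ANOVA 85–93%, repeated-measures ANOVA 94–100%.
- 7-point rise (10% of an assumed baseline of 70): one-way ANOVA 41–49%, repeated-measures ANOVA 66–97%.

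If all 60 infants can be analysed, pooled Spearman still rejects a true null 0.2–14% of the time. Its power for 10 points at SD 5 is 70–71%, against about 100% for within-infant correlation.

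A separate simulation with ρ of 0.5 to 0.9 and starting SD up to 8 mm Hg showed the same pattern. Pooled Spearman rejected from near 0% to about 17%, one-way ANOVA 0–0.4%, and repeated-measures ANOVA 4–6%.

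**The case against.** - **The ANOVA is left open, not wrong.** A repeated-measures ANOVA is an ANOVA, and its terms are often left to an analysis plan, which may exist unseen. This stands for the ANOVA on its own. It does not help Spearman, which the protocol chose and which no later detail can give an infant term.
- **A one-way ANOVA would do limited harm.** It is conservative and keeps 85–93% power at the planning effect. This also stands. The larger loss needs a smaller true rise, and the 7-point case rests on an assumed baseline.
- **Pooling is not stated, and Spearman is not given a decision rule.** True, so the point is conditional. The alternatives serve no better: within one step, Spearman compares different infants; on per-infant changes, the EtCO₂ change is nearly fixed by design, leaving little to correlate.
- **The direction of the Spearman error rests on an assumed spread.** It does. Near a starting SD of 3 mm Hg the error rate is close to 5%, and the exclusion of hypercapnic lung disease makes the largest spreads less likely. Power at SD 3 is still 72–73% against 96–100%.
- **The sample size points to neither analysis.** A total of 36 equals a paired design with zero correlation, so it over-sizes rather than under-sizes. Agreed: it does not prove pooling; it only fails to establish a paired plan.
- **The within-infant methods have limits too.** Repeated-measures correlation assumes a common slope. When responses varied between infants (assumed SD 8–10 points per 10 mm Hg), it rejected a true null 6–8% of the time. Blood-pressure correction between the first and later series could also mix with the CO₂ effect, but that affects any analysis of these series.

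**Conclusion.** The concern holds, and section 5 should be corrected before analysis. The firm part needs no assumed number: the design gives three readings per infant, Spearman has no infant term, and the ANOVA is not tied to a within-infant factor. If readings are pooled, any within-infant correlation above zero makes the one-way ANOVA p-value too large. The Spearman p-value can err in either direction.

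The size is conditional on pooling, on within-infant correlation of 0.3–0.7, and on the spread of starting EtCO₂, none of which the protocol states. Over those ranges the real Spearman error rate runs from 0.2% to 14% at nominal 5%. Recruiting more infants does not repair it. Confidence is high on the mismatch; the exact error rate is unknown.

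**What to change.** In section 5:

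1. State that the ANOVA is a repeated-measures ANOVA, or a linear mixed model with infant as random effect. EtCO₂ step (post-induction, +5, +10 mm Hg) is the within-infant factor, applied to the anaesthetised series for rSO₂c and for each velocity. Confirm at the same time that the two 5 mm Hg rises are successive, since section 3 does not say so outright.
2. Replace the pooled Spearman coefficient with a repeated-measures (within-infant) correlation, or with the EtCO₂ slope from the same model. If responses are expected to differ between infants, a t-test on per-infant slopes is a simple option; it stayed at 4–6% in the separate simulation, which used a common slope.

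The cost is analysis wording only: no new data, no more infants, and no change to the objectives or procedures.

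### The sample-size statement gives a beta risk of 90%, a power of 10%; the 36 subjects correspond to a beta of 10%

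*Protocol*

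**What the plan says.** Section 5 of the protocol has a single sample-size calculation. The planned effect is that a rise of 10 mm Hg in EtCO₂ "could result in a relative increase in rSO_2c of +10" per cent. The variability is taken "with a mean standard deviation of rSO_2c of 13% observed in the previous studies". The result, with its error rates, is "we calculate the necessary number of subjects to be 36 (alpha risk = 5%; beta risk = 90" per cent. Enrolment is then set higher: "To ensure that we will be able to analyze 36 patients, we hope to include 60 patients in the study".

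No other part of the protocol states a power, gives beta again or corrects it. Whether alpha is one-sided or two-sided is not stated.

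**The concern.** The sentence presents alpha and beta side by side as risks, that is, as error probabilities. Read that way, the study accepts a 90% chance of failing to detect the increase it is designed to find. No one would plan such a study, and the stated number of subjects does not fit it.

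Alpha and beta are the only error rates in the protocol, and this sentence is the only justification for analysing 36 infants. The participants are under 6 months old and undergo ventilation changes made for the study. An ethics committee weighing that burden needs to know the chance that the study will answer its question, and the printed figure is the complement of the intended one. The error could also be copied into a later analysis plan or report.

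**Working it through.** **Inputs, all from section 5 unless noted**

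- Effect: 10 (a relative increase in rSO₂c of 10%). No baseline rSO₂c is given, so it is taken on the same scale as the standard deviation.
- Standard deviation: 13.
- Alpha: 5%; two-sided is assumed first.
- Beta: 90% as printed, so power 10%.
- Stated result: 36.

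**Formula** (two means, normal approximation)

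n = 2 × (z for alpha + z for power)² × (SD / effect)², with 2 × (13/10)² = 3.38.

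**Reproducing the plan's figure, beta 10% (power 90%)**

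n = 3.38 × (1.9600 + 1.2816)² = 3.38 × 10.508 = 35.5, rounded up to 36. This matches exactly.

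The power with 36 is 90.4% by the normal approximation and 89.6% by the noncentral t, so beta is about 10%.

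**Beta as printed, 90% (power 10%)**

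n = 3.38 × (1.9600 − 1.2816)² = 3.38 × 0.4603 = 1.56, rounded up to 2. The t distribution gives 3.

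**Other combinations, same effect and standard deviation**

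| Power | Alpha 5% | n, normal formula | n, t distribution |
|---|---|---|---|
| 10% (as printed) | two-sided | 2 | 3 |
| 10% (as printed) | one-sided | 1 | 2 |
| 80% | two-sided | 27 | 28 |
| 80% | one-sided | 21 | 22 |
| 90% | two-sided | **36** | 37 |
| 90% | one-sided | 29 | 30 |

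**Paired formula**, n = (z for alpha + z for power)² × (SD of change / effect)², two-sided

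- SD of change 13: n = 18 at 90% power and 0.78 at 10% power.
- SD of change 13√2 (no correlation within an infant): n = 36 at 90% power and 1.56 at 10% power.

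**If the 10% is relative and the standard deviation is in absolute points.** Assume a baseline rSO₂c of 60 to 80; the protocol gives none. The difference is then 6 to 8 points, and a beta of 90% requires 5 to 3 per group. That is still nowhere near 36.

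**The reverse check.** With 36 per group, a power of 10% corresponds to a difference of 13 × √(2/36) × (1.9600 − 1.2816) = 2.1, not 10.

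**The case against.** The strongest reply is that this is a slip of terminology with no effect on the design. A statistical reader sees at once that 90% is the power, and no enrolment figure, analysis or timetable moves when the word is corrected. That is true, and it limits the weight of the point. It does not make the sentence right: the reader has to redo the calculation to learn what was meant.

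A second reply is that 36 does not identify a beta of 10% without further assumptions. The match needs a two-sided alpha, the 10% increase treated as 10 units on the scale of the standard deviation, and the formula for two independent groups. Other readings attach other powers to 36:

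- One-sided alpha, two groups: about 94.7%.
- Paired, SD of change 13, difference 10: 99.4%.
- Paired, SD of change 13, with an assumed baseline near 61 and so a difference of 6.1: about 80% by the normal approximation.

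This stands as a qualification: the exact match holds for the two-sided, two-sample normal formula, and the two-sided alpha is inferred from it. None of these powers is close to 10%.

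A third reply is that beta does not determine the 60 enrolled. That also stands. The step from 36 to 60 is an allowance for infants who cannot be analysed, with no rate given.

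Finally, 36 is a per-group size under the matching formula, whereas the study measures the same infants repeatedly (section 3, Methodology: "two series of measurements with a MAP greater than 35 mm Hg will be made after modifications to the ventilation"). That is a separate question about the choice of formula and does not bear on the mislabelled beta.

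**Conclusion.** The concern holds. The stated beta of 90% contradicts the stated 36 subjects under every reading tried: taken literally, it gives 5 or fewer. Under the two-sided, two-sample normal formula with effect 10 and standard deviation 13, a beta of 10% gives exactly 36, so the 90% is almost certainly the power. The printed miss risk is nine times the intended one (90% against 10%).

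The conclusion that the printed figure is wrong does not depend on the sidedness of alpha or on whether the formula is paired. The identification of 10% as the intended value does rest on those choices, and the investigator can confirm it. The correction should be made because it concerns the study's stated chance of success, but it leaves 36 and 60 as they are.

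**What to change.** In section 5, replace the error rates with: alpha risk = 5%, two-sided; beta risk = 10% (power 90%). The investigator should first confirm from the original calculation that alpha was two-sided, since the protocol does not say so. If the calculation is later recast for repeated measurements in the same infant, the corrected beta should be carried into it.

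The cost is a one-line correction, with no change to the numbers analysed or enrolled, the sensors supplied or the timetable.

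### The MAP condition applies to the raised-EtCO2 series but not to the post-induction series, so an ANOVA by EtCO2 that is not paired within infants can inflate the CO2 effect

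*Protocol*

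**What the plan says.** Protocol section 3 (Description of study) sets out the series in order. After the awake reading comes the post-induction series: "After the induction of general anesthesia and airway control, a series of measurements (Doppler and cerebral oxygen saturation) will be made". No MAP condition is attached to it. The text then turns to low pressure: "a bolus of ephedrine, 0.5 mg/kg, will be administered if the MAP is less than 35 mm Hg after the induction of anesthesia". The raised-EtCO2 steps follow, with a MAP condition: "two series of measurements with a MAP greater than 35 mm Hg will be made after modifications to the ventilation", each step aiming at a rise of 5 mm Hg in EtCO2.

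Section 2 words the primary objective as the impact of varying EtCO2 "on CBF and cerebral oxygenation with a MAP of between 35 and 40 mm Hg in infants under 6 months of age". This range has an upper limit, which the condition in section 3 lacks.

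Section 5 names two analyses: Spearman correlations of the perfusion parameters with EtCO2, and an ANOVA of rSO2c and velocities by EtCO2. It does not say whether readings are paired within infant or which series enter. On size it says "we calculate the necessary number of subjects to be 36 (alpha risk = 5%; beta risk = 90"%), and then "To ensure that we will be able to analyze 36 patients, we hope to include 60 patients in the study". No reason is given for the gap between 36 and 60.

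**The concern.** The CO2 effect is a comparison between series, and the two sides are collected under different rules. Every infant under anesthesia can supply a post-induction series. Only an infant with MAP above 35 mm Hg can supply a raised series that meets the text. Section 1 lists arterial pressure among the factors that influence cerebral blood flow and oxygenation, so an infant missing a raised series for this reason may well have lower readings to begin with.

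If readings are pooled by EtCO2 level, such infants pull down the post-induction mean and are absent from the raised means. The difference between levels then contains a contribution from who was measured as well as from CO2. It runs in the direction the study expects, so it would look like confirmation. A Spearman coefficient over all pooled readings is exposed in the same way.

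**Working it through.** **1. The plan's own figure.** Inputs from section 5: a difference of 10 ("could result in a relative increase in rSO_2c of +10"%), an SD of 13 ("mean standard deviation of rSO_2c of 13% observed in the previous studies"), and alpha 5%. Two readings are needed to reproduce 36: the stated beta of 90% is taken as power of 90%, and the 10% is taken as 10 points, in the same units as the SD. For two independent groups, two-sided:

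n per group = 2 × [13 × (1.960 + 1.282) / 10]² = 35.5, rounded up to 36.

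For a paired comparison with within-infant correlation ρ, the number of infants is 2(1 − ρ) × [13 × (1.960 + 1.282) / 10]². This gives 35.5 at ρ = 0 and 17.8, so 18, at ρ = 0.5. The figure of 36 therefore matches a calculation that takes no credit for pairing. This does not prove that the ANOVA will be unpaired, but nothing in section 5 points the other way.

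**2. The reserve.** (60 − 36) / 60 = 40%, and 36 / (1 − 0.40) = 60. For comparison, a 10% allowance gives 36 / 0.90 = 40 infants and a 20% allowance gives 36 / 0.80 = 45. The protocol does not link the reserve to MAP.

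**3. Bias of a pooled comparison.** The protocol gives neither the share of infants who would lack a raised series nor rSO2c by MAP, so both are assumptions here:

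- f = share of infants without a raised series
- g = points by which their post-induction rSO2c lies below that of the others
- μ = post-induction mean of infants who have the raised series
- Δ = true CO2 effect, taken as the planned 10 points

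Post-induction mean, all infants: (1 − f)μ + f(μ − g) = μ − fg.

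Raised-EtCO2 mean, remaining infants: μ + Δ.

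Pooled difference: Δ + fg.

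| f | g = 0 | g = 5 | g = 10 |
|---|---|---|---|
| 0 | 10 | 10 | 10 |
| 0.1 | 10 | 10.5 | 11 |
| 0.2 | 10 | 11 | 12 |
| 0.4 | 10 | 12 | 14 |

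The excess runs from zero to 4 points, the latter being 4 / 10 = 40% of the planned effect. The row f = 0.4 treats the whole reserve as loss and is an extreme.

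**4. Within-infant contrast.** Among infants with both series, (μ + Δ) − μ = Δ, whatever f and g are. Pairing removes the bias from baseline selection. It does not remove the effect of a change in MAP, or of an ephedrine bolus, between an infant's own series. For that reason MAP has to be on record for each series.

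**The case against.** The other side has several sound points.

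- *A reader might infer that the plan keeps 36 infants and discards 24.* The text does not say so. It gives 36 as the number needed and 60 as the hoped-for enrolment that secures it, and section 6 plans for n = 60.
- *A reader might infer that infants with persistently low MAP leave the study, or that the investigator decides after seeing the readings who can be analysed.* No exit rule and no such selection are stated. The MAP condition can also be read as a state to be reached before measuring. The study diagram announced in section 3 is not in the text available to me and may say more. What stands is only that an infant whose MAP does not stay above 35 mm Hg cannot supply a conforming raised series.
- *A reader might infer that the result fails to represent infants under 6 months in general.* The objective is itself limited to MAP between 35 and 40 mm Hg, so infants who never reach that range fall outside the question. This largely removes the generalisability complaint. It does not excuse a post-induction comparator without the same restriction.
- *The ANOVA may be a repeated-measures one.* That is compatible with section 5, and the bias in step 3 would then not arise among infants with complete series. The protocol does not say it, and the sample size takes no credit for it.
- *Analysis sets and missing data belong in a SAP.* Granted: their absence from the protocol is not the point. The point rests on what the protocol fixes, namely a MAP condition on one side of the comparison and an analysis by EtCO2 level.

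**Conclusion.** The point holds in a limited form. Followed as written, sections 3 and 5 permit a comparison of EtCO2 level means that come from different infants and different MAP states, and the resulting bias favours the expected finding.

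Its size is not derivable from the documents. It equals f × g under the assumptions above: zero if no infant lacks a raised series or if the analysis is within infants, 0.5 points at f = 0.1 and g = 5, and 4 points at f = 0.4 and g = 10. A firmer figure is tempting: treat 20% to 40% of infants as lost purely for low MAP and assume a correlation between MAP and rSO2c. The protocol supports neither the loss rate, nor its cause, nor the correlation, so no such figure should be quoted as the expected bias.

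Separately, the MAP range in the objective and the MAP condition in section 3 do not agree, and the condition covers only part of the comparison.

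**What to change.** In section 5:

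- Estimate the EtCO2 effect on rSO2c and velocities from within-infant changes on the achieved EtCO2, using a repeated-measures or mixed model with infant as a factor. Entering infant as a fixed factor makes the estimate rest on within-infant changes alone. A classical repeated-measures ANOVA that drops infants with any missing series would lose those with a single raised step. The pooled Spearman coefficient can stay as a description.
- Analyse every infant with a post-induction series and at least one raised-EtCO2 series.
- Record the measured MAP with each series.
- Report how many infants lacked each raised series and why (MAP, technical, surgical timing), and give the reason for the reserve from 36 to 60.

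The sponsor must also reconcile the MAP range in section 2 with the condition in section 3, and state whether it covers the post-induction series. Which condition is right is a clinical matter for the sponsor.

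The cost is a few sentences and one reason-for-missing field on the data form, with no extra infants or procedures. By step 1 of the working, pairing does not raise the required number for any correlation of zero or more. The downside is that infants with one step contribute less information, and the number analysed is no longer a fixed 36.
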